## **11 TRIAL DESIGN**

### **11.1 OVERALL DESIGN**

This is a phase IV, multi-center, prospective, parallel-group, open-label, randomized clinical study in one hundred and twenty-six (126) subjects [neonates and infants (0-9 months)] diagnosed with CH. Subjects will be randomized in a 2:1 ratio to Treatment (Tirosint®-SOL) or Control (conventional therapy with crushed LT4 tablets).

Newly diagnosed neonates will be randomly assigned to start therapy with LT4 at the initial dose recommended by the SOC. Infants already on LT4 therapy will continue at the same daily dose within the randomly assigned treatment group (dose adjustments are allowed, if needed based on laboratory parameters and clinical response).

Once enrolled, subjects will be treated and followed for 12 months ( $\pm 1.5$  months), participating in 7-8 study visits, consisting of 6-7 in-clinic and 1-2 TM visits (or more if follow-up visits are required). The total number of visits depends on the age at inclusion as reported in **Table 2**. In-clinic visits are performed 3-4 weeks after randomization, when the subject is 4, 6, and 9 months of age, then every 3 months as required depending on the age at the inclusion. TM visits will be performed 1-2 weeks after randomization, when the subject is 2 months of age, if applicable, and any time an additional follow-up is required for TSH and T4 monitoring.

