### 13.1.2 DOSAGE AND ADMINISTRATION

Both products will be used and dosed according to the USPI and SOC.

The dose administered will be based on the subject's BW and age, and adjusted based on clinical response and laboratory parameters according to SOC and PI's judgement.

These procedures are informed by the main treatment guidelines, as well as in the USPI of Tirosint®-SOL and LT4 tablets ([Synthroid USPI](#), [Tirosint®-SOL USPI](#)), as described in **Section 11.3**.

**Further to these general principles, Investigators are required to follow the SOC in order to define the correct dose and treatment goal for each subject.**

Initial Dosing in newly diagnosed neonates:

- Replacement therapy with LT4 should be started as promptly as possible upon diagnosis of CH.
- **Inclusion in the study must not delay the start of LT4 treatment.**
- Initial neonate LT4 dose should be between 10-15 mcg/kg;
- The initial dose should take into account the severity of the disease; and
- The goal of therapy should be to normalize FT4 into the upper half of the reference range and TSH within the reference range (it is suggested, within the mid- to lower half of the reference range whenever appropriate).

Initial Dosing in infants already under LT4 therapy:

- Subjects will be switched directly from crushed LT4 tablets to Tirosint®-Sol or continue on crushed LT4 tablets, with **no treatment interruption**.
- Same dose used before screening should be maintained, if replacement is adequate at screening/inclusion; or
- Dose should be adjusted at inclusion, if needed based on laboratory parameters and clinical response.

Dosing throughout study in neonates and infants:

- Dose adjustments can be done whenever required throughout the study and will be defined based on the evaluation of T4 and TSH values and clinical response according to SOC; and
- Therapy should aim to maintain serum TSH concentration in the age specific laboratory reference range (it is suggested, to target the mid- to lower half of the reference range whenever appropriate) and serum T4 concentration in the upper half of the age specific laboratory reference range.

If dose fine tuning is required, which cannot be obtained with the available strengths, alternating two strengths over the course of the week may be allowed. All dosing schemes must be documented in the EDC.

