3 STUDY DESIGN

This is a multi-center, prospective, parallel-group, open-label, randomized clinical study in one hundred and twenty-six (126) subjects (neonates and infants diagnosed with congenital hypothyroidism (CH)).

Subjects will be randomized in a 2:1 ratio to Treatment (Tirosint®-SOL) or Control (levothyroxine sodium crushed tablets).

Newly diagnosed neonates will be randomly assigned to start therapy with Levothyroxine (LT4) at the initial dose recommended by the Standard of Care.

Infants already on LT4 therapy will continue at the same daily dose within the randomly assigned treatment group (dose adjustments are allowed, if needed based on laboratory parameters and clinical response).

Once enrolled, subjects will be treated and followed for 12 months (± 1.5 months), participating in 7-8 study visits, consisting of 6-7 in-clinic and 1-2 (or more if follow-up

visits are required) telemedicine visits. The total number of visits depends on the age at inclusion as reported in the Tables 1 Schedule of Evaluations and Table 2 Outline of Visit Schedule based on Age of the study protocol.

In-clinic visits are performed between 3-4 weeks after randomization, when the subject is 4, 6, and 9 months of age, and then every 3 months as required depending on the age at the inclusion. Telemedicine visits will be performed between 1-2 weeks after randomization, when the subject is 2 months of age, if applicable, and any time an additional follow-up is required for TSH and thyroxine (T4) monitoring.

For further details refer to Study Protocol n. 20US-T414 final version v2.0, Release date: September 7, 2023.

The study was originally planned to enroll a total number of 126 subjects (84 Treatment and 42 Control), expected between September 2021 and July 2022. Despite the extension of the study timeline, a protocol amendment and the efforts by the sites, the enrollment (screening) was closed on 31 March 2024 with a total of 31 randomized subjects, since reaching the enrollment target appeared no longer practicable within reasonable timeframe.

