3.4 CHANGES FROM STUDY PROTOCOL

Section 19.2 Population for analysis:

The following subject populations were foreseen:

- Full Analysis Set (FAS): all randomized subjects;
- Per Protocol Set (PPS): all randomized subjects with no major protocol deviations; and
- Safety Analysis Set (SAF): all randomized subjects who received at least 1 dose of study medication.

Due to the premature termination of the study and the limited sample size the Per Protocol Set will not be considered for the final analysis.

Section 19.3.1 General Statistical Methods:

Due to the fast changing measurements in the specific population, in relation to growth, the last observation carried forward (LOCF) method will not be used to deal with missing data or in the case of early study discontinuation and missing data will not be replaced.

Section 19.3.2 Efficacy outcomes:

Due to the premature termination of the study and limited sample size all the efficacy analyses will be considered exploratory. LT4 dose/kg, laboratory parameters (TSH and FT4), “Parents’ Satisfaction Questionnaire” will be analyzed with a mixed model adjusted with Kenward-Roger method and considering as first choice the unstructured covariate matrix (other matrixes will be considered if there will be convergence problems). Variables newly diagnosed neonates vs infants already on LT4 therapy and center will not be considered in the models. Normal distribution for LT4 dose/kg, laboratory parameters (TSH and FT4), “Parents’ Satisfaction Questionnaire” will be tested with Shapiro Wilks, if data result not distributed as a normal distribution a log transformation will be applied. LT4 dose/kg, TSH and FT4 levels and Parents’ Satisfaction Questionnaire score at each visit will be compared between treatment groups by Wilcoxon Mann-Whitney test.

Section 19.3.3 Exploratory outcomes:

Time to TSH and FT4 normalization in the neonates will not be evaluated between the treatment groups due to the low number of neonates enrolled (3 randomized to Tirosint-SOL and only 1 to Control).

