9.3 DEMOGRAPHIC AND SCREENING/BASELINE CHARACTERISTICS

Descriptive statistics of baseline characteristics will be presented for the Full Analysis Set (FAS).

Subjects baseline characteristics will include:

- Demographic data: age at screening, age at randomization, age class (infant or neonates), gestational age, weight at birth, sex, race, ethnicity, length at screening, weight at screening, BMI at screening, head circumference at screening, TSH (mIU/L) and T-4 FREE (pmol/L) levels at CH diagnosis.
- LT4 dose: LT4 dose (mcg/kg/day) at screening (for infants only)
- Hormonal status: TSH (mIU/L) and T-4 FREE (pmol/L) levels at screening (for infants only).
- Vital signs: pulse and temperature at screening.
- Physical examination: abnormal body systems at screening.
- Signs and symptoms of hypo and hyper thyroidism: category (hypothyroidism or hyperthyroidism) and sign or symptom at screening.
- Nutritional intake: breast milk, cow's milk, formula milk, baby food or adult-like food at screening.
- Medical History: those will be summarized by System Organ Class (SOC) and Preferred Term (PT).
- Previous Medications: All previous medications will be summarized by Anatomical Therapeutic Chemical (ATC) level 2 and preferred drug name.

Age at screening, age at randomization, gestational age, weight at birth, length at screening, weight at screening, head circumference at screening, TSH (mIU/L) and T-4 FREE (pmol/L) levels at CH diagnosis, TSH (mIU/L) and T-4 FREE (pmol/L) levels at screening (for infants

only), and LT4 dose (mcg/kg/day) at screening (for infants only) differences between treatment groups will be evaluated using Wilcoxon test.

Sex, ethnicity and race will be compared between treatment groups at each visit using a Chi-squared test or, when the expected values in any of the cells of a contingency table are below 5 or the total number of observations is less than 20, Fisher exact test as appropriate.

The demographic data analysis will be repeated stratified on neonates and infants.

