9.4.1 Primary efficacy analysis

LT4 dose/kg

The LT4 dose/kg will be calculated based on the daily LT4 dose used in the time period preceding the visit and the body weight measured during the visit. When dosing schedules alternating strengths over the course of the week are used, the daily dose will be calculated as the average daily dose on a weekly basis.

The LT4 dose/kg required to maintain TSH in target range will be analyzed at 12 months of age visit (V8) and when the subject is 2, 4, 6, 9, 15, 18 and 21 months of age (V4, V5, V6, V7, V9, V10, V11) by means of analysis of covariance (mixed model), including treatment group, age at randomization and interactions between visit and treatment group as covariates. Treatment effect at each visit will be estimated.

Normal distribution for LT4 dose/kg will be tested with Shapiro Wilks, if data result not to be distributed as a normal distribution a log transformation will be applied.

The mixed model will be adjusted with Kenward-Roger method and the unconstructed covariance matrix will be used as first choice (other matrixes will be considered if there will be convergence problems).

Summary descriptive statistics will be provided for LT4 dose/kg and results at each visit will be compared between treatment groups by Wilcoxon Mann-Whitney test. This analysis will also be repeated stratified on neonates and infants.

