9.4.2 Secondary efficacy analyses

Laboratory parameters (TSH and FT4)

Laboratory parameters (TSH and FT4) will be analysed at each time point by means of analysis of covariance (mixed model), including basal value, treatment group, age at randomization and interactions between visit and treatment group as covariate.

Normal distribution for TSH and FT4 will be tested with Shapiro Wilks, if data result not to be distributed as a normal distribution a log transformation will be applied.

The mixed model will be adjusted with Kenward-Roger method and the unconstructed covariance matrix will be used as first choice (other matrixes will be considered if there will be convergence problems).

Summary descriptive statistics will be provided for each laboratory parameter. TSH and FT4 levels at each visit will also be compared between treatment groups by Wilcoxon Mann-Whitney test. This analysis will also be repeated stratified on neonates and infants.

Laboratory data will also be listed with clinically significant information.

TSH values above 4.5 mU/L

The events of TSH values above 4.5 mU/L will be compared between treatment groups at each visit and aggregate from Visit 2 to the last available visit using a Chi-squared test or, when the expected values in any of the cells of a contingency table are below 5 or the total number of observations is less than 20, Fisher exact test as appropriate.

FT4 values below the middle of the laboratory normal range

The events of FT4 values below the middle of the laboratory normal range will be compared between treatment groups at each visit and aggregate from Visit 2 to the last available visit using a Chi-squared test or, when the expected values in any of the cells of a contingency table are below 5 or the total number of observations is less than 20, Fisher exact test as appropriate.

Parent satisfaction assessed by “Parents’ Satisfaction Questionnaire”

Parent satisfaction assessed by “Parents’ Satisfaction Questionnaire” score at V3, V5, V6, V7, V8, V9, V10, V11 will be analyzed by means of analysis of covariance (mixed model), including treatment age at randomization and interactions between visit and treatment group as covariate.

Normal distribution for Parents’ Satisfaction Questionnaire score will be tested with Shapiro Wilks, if data results not be distributed as a normal distribution a log transformation will be applied.

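### The primary dose/kg model omits the infants' LT4 dose/kg at screening, which costs precision and leaves any chance entry-dose imbalance uncorrected

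*SAP*

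**What the plan says.** SAP 9.4.1 analyses LT4 dose/kg, the only primary efficacy variable, in a mixed model at V4 to V11, "including treatment group, age at randomization and interactions between visit and treatment group as covariates". No entry-dose term appears there, in SAP 3.4, or in the protocol's own dose model (Protocol 19.3.2). Dose/kg is also compared at each visit by a Wilcoxon test, repeated separately in neonates and infants; these tests are unadjusted.

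The entry dose is among the baseline characteristics in SAP 9.3: "LT4 dose: LT4 dose (mcg/kg/day) at screening (for infants only"). The same section compares it between arms: "and LT4 dose (mcg/kg/day) at screening (for infants only) differences between treatment groups will be evaluated using Wilcoxon test".

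The secondary TSH and FT4 models in SAP 9.4.2 do adjust for baseline, "including basal value, treatment group, age at randomization and interactions between visit and treatment group as covariate".

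On carry-over, Protocol 11.1 says: "Infants already on LT4 therapy will continue at the same daily dose within the randomly assigned treatment group". Protocol 13.1.2 adds: "Same dose used before screening should be maintained, if replacement is adequate at screening/inclusion"; otherwise the dose is adjusted at inclusion.

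Enrolment closed "with a total of 31 randomized subjects" (SAP 3). The neonates were "3 randomized to Tirosint-SOL and only 1 to Control" (SAP 3.4).

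**The concern.** For most children in this trial the primary variable has a baseline value. It is already in the database, and it is where on-study dosing normally starts. The plan tabulates it and tests it between arms, but does not use it in the primary model. A between-arm test can display an imbalance but cannot correct one, and with about 9 Control infants it has little power to flag one.

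Age at randomization is the only prognostic covariate left, because SAP 3.4 removes age class and center. Age cannot represent differences in requirement between children of the same age. With about 10 Control children, two things are at stake: the width of the interval for the primary contrast, and how far a chance entry-dose difference moves the estimate.

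**Working it through.** **Inputs from the documents.** 31 randomised (SAP 3). Neonates 3 + 1 = 4 (SAP 3.4), so infants 31 − 4 = 27. Allocation 2:1. SD 2 mcg/kg, mean 6 mcg/kg/day, difference 20% of 6 = 1.2 mcg/kg, two-sided 0.05 (SAP 3.2). Every row of Protocol Table 2 includes V8, so all 31 could contribute there.

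**Assumptions.** The infants' split is not given; 18:9 is assumed, which with 3:1 neonates makes 21:10. Entry SD is taken as 2, the same as at follow-up. The correlation r of entry dose/kg with V8 dose/kg, given age, is not in the documents, so a range is shown. No child is missing at V8 and no screening dose is missing. A single-visit ANCOVA stands in for the mixed model.

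**1. The plan's own figure.** The normal formula gives a Control group of (1.96 + 0.8416)² × 2² × (1 + 1/2) / 1.2² = 32.7, so 33, and 99 in total. The noncentral t distribution gives 80.8% power at 68:34. The stated 102 reproduces.

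**2. Precision at 31 children.** By formula, the half-width with treatment and age in the model (28 df) is about 2.048 × 2 × √(1/21 + 1/10) = 1.57. Simulation of the V8 model gives 1.58. The adjusted model adds an infant indicator and an infant-centred entry dose:

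| Model | r | 95% CI half-width (mcg/kg) | Power for 1.2 |
|---|---|---|---|
| Planned | any | 1.58 | 32% |
| Adjusted | 0 | 1.62 | 30% |
| Adjusted | 0.3 | 1.56 | 33% |
| Adjusted | 0.5 | 1.43 | 38% |
| Adjusted | 0.7 | 1.23 | 49% |

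Coverage is about 95% in both models. The interval narrows by (1.58 − 1.43)/1.58 = 9% at r = 0.5 and (1.58 − 1.23)/1.58 = 22% at r = 0.7. It widens by about 3% at r = 0. Break-even lies at r of about 0.2 to 0.3.

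**3. Infants only (18:9).** The half-width is 1.72 unadjusted, against 1.76, 1.68, 1.53 and 1.26 adjusted at r = 0, 0.3, 0.5 and 0.7.

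**4. Size of a chance entry imbalance.** Among infants its standard error is 2 × √(1/18 + 1/9) = 0.82 mcg/kg. A difference of 1.0 or more in either direction then has probability about 22%.

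**5. Effect on the planned 31-child contrast.** Infants are 18 of 21 in one arm and 9 of 10 in the other. Ignoring the age term, a one-standard-error imbalance moves the unadjusted contrast by r × 2 × √(18/21² + 9/10²) = 0.72r:
- r = 0.3: 0.22 mcg/kg, 18% of 1.2
- r = 0.5: 0.36 mcg/kg, 30% of 1.2
- r = 0.7: 0.51 mcg/kg, 42% of 1.2

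In simulation the adjusted contrast does not move with the imbalance (slope about 0).

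**The case against.** The strongest reply is that nothing here is invalid. Allocation is randomised, so the planned estimate is unbiased, its type I error holds, and its interval already allows for chance imbalance. That stands. A reader might infer that an entry imbalance would be reported in full as a formulation effect. The documents do not support this: carry-over is in proportion to r, and the distortion is conditional on the imbalance that occurs.

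Second, r is unknown, and there are reasons for it to be modest at V8. Doses may be adjusted at inclusion and throughout, weight rises while a dose is held, and age is already in the model. This also stands, and the gain at r = 0.3 is negligible.

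Third, a reader might treat the infants as stabilised and the question as change from entry. The text goes less far. Three weeks of prior LT4 suffice (Protocol 12.1), and the stated objective is the dose required to keep TSH in target. Adjustment for the entry dose serves that objective without redefining it.

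Fourth, efficacy is declared exploratory (SAP 3.4 and 9.4), so no confirmatory decision turns on this term, and even at r = 0.7 the half-width of 1.23 still exceeds 1.2. True, but estimates and intervals are then the main product, which favours making them as informative as the data allow.

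Fifth, the SAP already shows the entry dose and repeats the dose/kg comparison in infants. Both help the reader, but neither adjusts. Nor did the SAP drop a promised term, since the protocol model had none.

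**Conclusion.** The point holds as one of efficiency and conditional protection, not of bias. The primary model leaves out a baseline value that the plan collects for infants, 27 of 31 children if complete, while the secondary laboratory models use theirs. The plan gives no reason for the difference. The gain runs from nothing below r of about 0.2 to 0.3 to an interval about 9% narrower at r = 0.5 and 22% narrower at r = 0.7. Without the term, a one-standard-error entry imbalance shifts the estimate by about 0.22 to 0.51 mcg/kg over r = 0.3 to 0.7. The omission is certain from the text. The size of the gain is not: it rests on r, the 18:9 split, an entry SD of 2 and complete data at V8.

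**What to change.** In SAP 9.4.1, add LT4 dose/kg before screening as a covariate. Specify the pre-screening dose, not the dose set at Visit 1: in Protocol 16.1 the dosing evaluation is listed after randomisation, and in an open-label trial that dose could be influenced by allocation. Keep the 4 neonates by adding the neonate/infant indicator and an infant-centred dose set to 0 for neonates. Show an infants-only version of the adjusted model as well. If outcome data have already been examined, keep the planned model, report the adjusted one beside it, and label it as added later.

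No new data are needed. The costs are two degrees of freedom, an interval about 3% wider if r is 0, and the loss of any infant without a screening dose, because SAP 8 does not replace missing values. The age-class term that SAP 3.4 removed also returns, with only one Control neonate and some overlap with age at randomization.

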9.4.2 Secondary efficacy analyses

Laboratory parameters (TSH and FT4)

Laboratory parameters (TSH and FT4) will be analysed at each time point by means of analysis of covariance (mixed model), including basal value, treatment group, age at randomization and interactions between visit and treatment group as covariate.

Normal distribution for TSH and FT4 will be tested with Shapiro Wilks, if data result not to be distributed as a normal distribution a log transformation will be applied.

The mixed model will be adjusted with Kenward-Roger method and the unconstructed covariance matrix will be used as first choice (other matrixes will be considered if there will be convergence problems).

Summary descriptive statistics will be provided for each laboratory parameter. TSH and FT4 levels at each visit will also be compared between treatment groups by Wilcoxon Mann-Whitney test. This analysis will also be repeated stratified on neonates and infants.

Laboratory data will also be listed with clinically significant information.

TSH values above 4.5 mU/L

The events of TSH values above 4.5 mU/L will be compared between treatment groups at each visit and aggregate from Visit 2 to the last available visit using a Chi-squared test or, when the expected values in any of the cells of a contingency table are below 5 or the total number of observations is less than 20, Fisher exact test as appropriate.

FT4 values below the middle of the laboratory normal range

The events of FT4 values below the middle of the laboratory normal range will be compared between treatment groups at each visit and aggregate from Visit 2 to the last available visit using a Chi-squared test or, when the expected values in any of the cells of a contingency table are below 5 or the total number of observations is less than 20, Fisher exact test as appropriate.

Parent satisfaction assessed by “Parents’ Satisfaction Questionnaire”

Parent satisfaction assessed by “Parents’ Satisfaction Questionnaire” score at V3, V5, V6, V7, V8, V9, V10, V11 will be analyzed by means of analysis of covariance (mixed model), including treatment age at randomization and interactions between visit and treatment group as covariate.

Normal distribution for Parents’ Satisfaction Questionnaire score will be tested with Shapiro Wilks, if data results not be distributed as a normal distribution a log transformation will be applied.

The mixed model will be adjusted with Kenward-Roger method and the unconstructed covariance matrix will be used as first choice (other matrixs will be considered if there will be convergence problems).

Summary descriptive statistics will be provided for Parents’ Satisfaction Questionnaire score and the results at each visit will also be compared between treatment groups by Wilcoxon Mann-Whitney test.

Caregiver Administered Children’s Acceptance Tool (CareCAT)

The subject medicine acceptance assessed by “Caregiver Administered Children’s Acceptance Tool (CareCAT)” will be analyzed during the first week, the third week, and the eighth week

of administration and analyzed by day in each week and by week comparing the treatment groups by means Cochran-Mantel-Haenszel χ^2 test. Descriptive statistics on aggregate CareCAT results overall and by week will also be provided.

Dose re-adjustment

The number of subjects who need a dose re-adjustment during the long-term follow-up phase (Visit 4 to Visit 11) of the study will be compared between treatment groups by means of Chi-squared test or, when the expected values in any of the cells of a contingency table are below 5 or the total number of observations is less than 20, Fisher exact test as appropriate.

Growth pattern

Summary descriptive statistics on length (cm), weight (Kg) and head circumference (cm) will be provided. Results at each visit for each parameter will be compared between treatment groups by Wilcoxon Mann-Whitney test.

Growth assessment parameters will also be listed with clinically significant information.

Signs and symptoms of hypo- and hyper-thyroidism

Number of subjects experiencing hypothyroidism/hyperthyroidism signs or symptoms will be summarized by hypothyroidism, hyperthyroidism and overall.

The number of subjects experiencing at least one sign or symptom will be compared between treatment groups using a Chi-squared test or, when the expected values in any of the cells of a contingency table are below 5 or the total number of observations is less than 20, Fisher exact test as appropriate.

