### 11.3.1 REFERENCE RANGES AND TARGET RANGES FOR DOSE ADJUSTMENT

It is not possible to define a globally accepted reference range for TSH, TT4 or FT4. TH levels change markedly during childhood and therefore the reference range should be adapted based on age ([Kapelari 2008](#)). In the present study, age-specific reference ranges provided by the sites' laboratories will be adopted.

For TSH the AAP Guidelines proposed a target range of 0.5 and 2.0 mU/L during the first 3 years of life ([AAP 2006](#)), but the recent revision proposes to target TSH within the age-specific reference range ([Rose 2023](#)). LaFranchi indicates target ranges for TSH on treatment should be <5 mU/L, optimally 0.5–2.0 mU/L ([LaFranchi 2011](#)). Most commonly therapy is aimed at maintaining the serum TSH in the reference range ([Van Trotsenberg 2021](#)) or in the mid- to lower half of the pediatric reference range ([Jonklaas 2014](#)). No target range will be defined for TSH in the frame of the present study, but replacement therapy should target to maintain TSH levels within the age-

specific reference range ([Rose 2023](#)) (it is suggested within the mid- to lower half of the reference range whenever appropriate).

For FT4 and TT4, AAP Guidelines reported target values for FT4 of 1.4 – 2.3 ng/dL (or 18-30 pmol/L), and for TT4 of 10 – 16 µg/dL (or 130 – 206 nmol/L) during the first 3 years of life ([AAP 2006](#)), but the recent revision does not provide any target range ([Rose 2023](#)). LaFranchi also provides an example of FT4 reference range of 0.8 – 2.3 ng/dL, with a target range of 1.4 – 2.3 ng/dL ([LaFranchi 2011](#)). Therapy is most commonly aimed at maintaining the serum T4 in the mid- to upper half of the pediatric reference range ([Jonklaas 2014](#)). Reference ranges may vary greatly from one laboratory to another depending on the analytical method used ([Spencer 2017](#)). Therefore, no target ranges will be defined for T4 in the frame of the present study, but replacement therapy should target to maintain FT4 levels in the upper half of the age-specific reference range ([Rose 2023](#)).

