## 15 STUDY ASSESSMENTS AND PROCEDURES

### 15.1 EFFICACY ASSESSMENTS

#### 15.1.1 LABORATORY PARAMETERS

Laboratory parameters evaluated in this study include:

- Thyroid Stimulating Hormone (TSH);
- Free Thyroxine (FT4); and
- Total Thyroxine (TT4), optional, at the discretion of the Investigator.

The analyses will be conducted on serum samples.

Blood samples for serum FT4, TT4 and TSH monitoring will be collected 0 (during the visit) to - 7 days before each visit (within the allowed visit time frame) to allow for adequate time to evaluate the measurements.

Blood samples should be collected at least 4 hours after the last LT4 administration or before taking the LT4 daily dose ([VanTrotsenberg 2021](#), [Rose 2023](#)). Whenever possible perform the collection in the same way and at the same time at each visit.

At each visit, 1-4 mL of blood will be collected; 7-32 mL of blood will be collected per subject for the entire study (7-8 time points). If considering a maximum of two additional unscheduled visits during the course of the study, a maximum of 40 mL of blood will be collected over one year.

A venipuncture sample should be collected by accessing the veins of the antecubital fossa (inside the elbow), in order to obtain serum. If unable to obtain from antecubital fossa, a heel or finger prick is preferable to no sample. This must be clearly specified on the request to the laboratory and results will have to be converted by the laboratory to serum equivalents. In exceptional cases, a subject's blood draw may be performed at a different location (e.g. laboratory patient service center), as per SOC.

- Each site will attempt to use the same laboratory throughout the study (main laboratory). Additional laboratories may be used, but, in order to reduce variability, these should be limited to not more than 3 analytical lab facilities per site (e.g. hospital lab and other providers of diagnostic services such as Quest and LabCorp).
- Each site will attempt to use the same laboratory for the same subject throughout the study.
- Laboratory sampling and analytical procedures should be followed.

- Local lab reference ranges will be collected and any change in reference ranges should be recorded in the EDC.

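### The continuous FT4 analyses pool values from several local laboratories with no laboratory or range adjustment; this costs precision, and a position-in-range analysis should be added

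*SAP*

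**What the plan says.** **The analysis.** SAP section 9.4.2 states: "Laboratory parameters (TSH and FT4) will be analysed at each time point by means of analysis of covariance (mixed model), including basal value". The full list of model terms reads "including basal value, treatment group, age at randomization and interactions between visit and treatment group as covariate". It adds that "TSH and FT4 levels at each visit will also be compared between treatment groups by Wilcoxon Mann-Whitney test". The only change of scale concerns non-normality: "if data result not to be distributed as a normal distribution a log transformation will be applied". The SAP gives FT4 in pmol/L (section 9.3).

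**Centre.** The protocol's covariance model (section 19.3.2) contained centre. SAP section 3.4 takes it out: "Variables newly diagnosed neonates vs infants already on LT4 therapy and center will not be considered in the models". Nothing replaces it.

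**The measurements.** Protocol section 11.3.1 says: "Reference ranges may vary greatly from one laboratory to another depending on the analytical method used". For that reason it sets no numeric T4 target and directs therapy to the upper half of the age-specific FT4 range. There may be up to 20 sites (protocol synopsis). On additional laboratories, protocol section 15.1.1 says "these should be limited to not more than 3 analytical lab facilities per site". Keeping a child at one laboratory is something sites attempt, not a requirement. The notes to Table 1 of the protocol accept a child's own routine results at Visit 1. The material for an adjustment exists: "Local lab reference ranges will be collected and any change in reference ranges should be recorded in the EDC".

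**What already uses the range.** SAP section 9.4.2 also compares, by visit and in aggregate, the events of FT4 below the middle of the laboratory's normal range.

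**The concern.** The protocol declines an absolute FT4 scale for treatment because assays differ, and the SAP then uses an absolute scale for the continuous FT4 analyses. The same concentration can lie above the middle of one laboratory's range and below the middle of another's. A child whose laboratory changes between baseline and follow-up can show a change that is only assay. At Visits 2 and 3, which are timed from treatment start and not from age, the unadjusted Wilcoxon test also mixes children whose age-specific ranges differ.

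The hormonal profile is one of the primary objectives, and only 31 children were randomised. In an exploratory analysis of that size the estimates and their intervals are the main product, so avoidable noise matters.

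**Working it through.** **The plan's own figure.** The documents give no sample size, power or SD for FT4. Their one calculation concerns LT4 dose: a difference of 20% of 6 = 1.2 mcg/kg/day with SD 2. At 34 and 68 children the t-test power is 80.8%, so the stated 102 reproduces. It does not bear on FT4.

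**Inputs from the documents.** 31 randomised, 2:1, stratified by site and age group (SAP sections 3 and 3.3). By rule, at most 20 × 3 = 60 laboratories; the number used is not given.

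**Assumed inputs.** Let *r* be the between-laboratory SD divided by the between-subject SD within a laboratory. The documents give no value, so *r* = 0.25, 0.5 and 1 are scenarios. Also assumed: 8, 15 or 20 laboratories, one per site; allocation in blocks of 3 within site; a baseline-to-visit correlation of 0.5.

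**Step 1: variance of the pooled values.** Inflation = 1 + *r*², and the equivalent number of children = 31/(1 + *r*²).

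| *r* | Inflation | 31/inflation |
|---|---|---|
| 0.25 | 1.06 | 29.2 |
| 0.5 | 1.25 | 24.8 |
| 1 | 2.00 | 15.5 |

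This ignores the basal value, and it ignores offsets that cancel between arms within a site.

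**Step 2: simulation of one visit with no treatment effect (2000 runs per scenario).** Units are within-laboratory SDs.

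| *r* | SD of arm difference from laboratories alone | Chance that this shift exceeds 0.25 |
|---|---|---|
| 0.25 | 0.04–0.07 | 0% |
| 0.5 | 0.08–0.13 | 0.2–5% |
| 1 | 0.15–0.25 | 10–31% |

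The mean shift is about 0 in every scenario.

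**Step 3: baseline-adjusted estimate at *r* = 1.** The SD of the treatment estimate is about 0.34 with laboratory offsets removed.

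- Baseline from the same laboratory: SD about 0.36, so the variance ratio is (0.36/0.34)² = 1.12.
- Baseline from a different laboratory: SD 0.40 to 0.46, so the ratio is (0.40/0.34)² = 1.38 to (0.46/0.34)² = 1.83.

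**Step 4: unadjusted difference at *r* = 1.** Its SD is 0.415 to 0.46, against about 0.38 without offsets. The variance ratio is (0.415/0.38)² = 1.19 to (0.46/0.38)² = 1.47. The factor of 2.00 in step 1 therefore describes the spread of the values and overstates the loss in the arm comparison.

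**Step 5: rejection under the null at *r* = 1.** Wilcoxon 1.6–2.2%. Baseline-adjusted model 4.3–5.0% (same laboratory) or 1.8–2.6% (different laboratory). None exceeds 5%. Where the rate falls well below 5%, the test is conservative and loses power.

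**The case against.** Five points on the other side deserve an answer.

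- **The range-based goal is already analysed.** This stands, and it confines the point to the continuous analyses. The mid-range event is binary, however, and discards information in a sample of 31.
- **Site stratification and the basal value deal with laboratory differences.** This stands in part. Randomisation removes systematic bias. The basal value absorbs much of a stable offset, but only when both samples come from one laboratory, and the Wilcoxon test has no such adjustment.
- **Centre would not have solved it.** This stands. With up to three laboratories per site, centre is a poor proxy for laboratory, and up to 19 centre parameters are hard to support with 31 children. Removing centre is openly declared and is not itself the fault.
- **Drift of FT4 with age is largely common to both arms.** This stands from Visit 4 on, where visits are fixed by age. It is weaker at Visits 2 and 3.
- **Local ranges are themselves imperfect.** This stands. Protocol section 11.2 says they are highly variable and do not always take proper account of age. It is a reason to add the scaled analysis and not to replace the planned one.

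A reader might infer that laboratory differences bias the treatment comparison or produce false positive findings. The documents do not support that, given site-stratified randomisation and the results in steps 2 and 5. A reader might also infer one or two children per site. The documents give an upper limit of 20 sites and not the number that randomised; with 8 sites it would be about 31/8 ≈ 4.

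**Conclusion.** The point holds as a loss of precision and a risk of chance imbalance in the mixed model and Wilcoxon tests of FT4. It does not reach the mid-range event, and all efficacy analyses are declared exploratory.

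The size cannot be fixed from the documents. It could be trivial (6% more variance at *r* = 0.25). At *r* = 1 it would be material where baseline and follow-up laboratories differ (about 40% to 80% more variance in the adjusted estimate), and modest where they are the same (about 10%). These figures rest on the assumed ratios, numbers of laboratories, block size and correlation, and on a single-visit model standing in for the repeated-measures one. The absence of systematic bias further assumes that the choice of laboratory after randomisation does not depend on the arm; nothing in the documents suggests that it does.

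Adding a range-scaled analysis is a cheap improvement. The planned analysis need not be abandoned.

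**What to change.** In SAP section 9.4.2:

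1. Add an analysis of FT4 position in range = (value − lower limit)/(upper limit − lower limit), using the range reported for that sample. The middle of the range is 0.5, and values above 1 are over range.
2. Use it as the outcome and, where the range was recorded, for the basal value, in the same mixed model and Wilcoxon tests. Ranges for outside results accepted at Visit 1 may be missing; report how many.
3. Exempt it from the log-transformation rule, since values below the lower limit are negative.
4. Flag samples whose laboratory gave no age-specific range, and exclude them in a sensitivity analysis.
5. Keep the planned pmol/L analysis, which serves a protocol outcome, and interpret the two together.

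The cost is one derived variable, a few lines of SAP text and an extra set of tables. The scaled result depends on the quality of the local ranges, as the mid-range event already does. SAP version 2.0 is dated March 2026, two years after enrolment closed in an open-label trial, so the addition should be labelled supportive and dated. If analysis has begun, it should be explained in the statistical report, as SAP section 1 provides for deviations.
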